Determine the impact of upper airway stimulation on peripheral arterial tonometry ratio related to obstructive episodes in this cohort of patients with moderate-severe obstructive sleep apnea

Hypothesis: The peripheral arterial tonometry ratio related to obstructive episodes will be improved with increasing levels of upper airway stimulation

Aim 2a

Determine the impact of upper airway stimulation on flow mediated dilation in this cohort of patients with moderate-severe obstructive sleep apnea

Hypothesis: The flow mediated dilation parameters will be improved at therapeutic levels of upper airway stimulation and returned to pre-operative levels after 30-day withdrawal period

Aim 2b

Determine the impact of upper airway stimulation on peripheral arterial stiffness in this cohort of patients with moderate-severe obstructive sleep apnea

Hypothesis: The peripheral arterial stiffness parameters will be improved at therapeutic levels of upper airway stimulation and returned to pre-operative levels after 30-day withdrawal period

Aim 2c

Determine the impact of upper airway stimulation on 24-hour ambulatory blood pressure in this cohort of patients with moderate-severe obstructive sleep apnea

Hypothesis: The 24-hour ambulatory blood pressure will be improved at therapeutic levels of upper airway stimulation and returned to pre-operative levels after 30-day withdrawal period

Aim 2d

Determine the impact of upper airway stimulation on serum biomarker profile in this cohort of patients with moderate-severe obstructive sleep apnea

Hypothesis: The serum biomarker profile will be improved at therapeutic levels of upper airway stimulation and returned to pre-operative levels after 30-day withdrawal period

6. Study Design and Methods

Each participant will undergo three sets of blood testing. Each set of testing will require travel to the Emory Clinical Cardiovascular Research Institute (ECCRI) facility at Woodruff Memorial Research Building on Clifton Campus. The subjects will be provided directions, lunch and parking vouchers for each visit. The subject will be registered at the EECRI facility each time and undergo fasting bloodwork.

Study Timeline

- Post-operative appointment: obtain consent for study enrollment (Day 1)
- WatchPAT baseline home sleep test (Night 1)
- Baseline 24-hour ambulatory blood pressure monitoring (Day 2-3)
- Baseline serum biomarkers/vascular testing (Day 15)
- Device Activation (Day 15)
- In-lab Polysomnography Titration (Day 45)

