- WatchPAT treatment home sleep test (Night 75)
- Clinic visit (Day 105)

- Treatment serum biomarkers/vascular testing, 24-hour ambulatory blood pressure monitoring (Day 105-106)
- Therapy Withdrawal (Day 106-135)
- WatchPAT withdrawal home sleep test (Night 135)
- Withdrawal serum biomarkers/vascular testing, 24-hour ambulatory blood pressure monitoring (Day 136-137)
- Therapy Reactivation (Day 137)

Risks

The risks from participating in the research include the release of confidential information.

Due to the research nature of this study there may be other risks that are currently unknown. For instance, in the future it may be possible to link genetic factors to medical problems that could possibly influence insurability and employability, either for yourself or for your immediate family. To prevent this from being a problem for you in the future, your blood samples and research results will be labeled with a study ID number and not your name. Therefore, there will be no direct linkage between your blood sample and your name. However, this code will allow researchers to link your clinical information with your blood sample, without knowing your name.

Blood testing and genetic testing: rarely, bleeding can occur around the site where we draw your blood. This is not dangerous, but, if it occurs, it could result in a small bruise. Skin tape reactions may occur in a small portion of allergic subjects, but generally well tolerated and causes no long-term side effects.

Blood flow measurements: The blood pressure inflation lasts for 5 minutes and can result in temporary feelings of numbness and pins and needles in the arm that last for one or two minutes. However, this is generally well tolerated and causes no long-term side effects. The blood flow measurement device worn for 24 hours is very well tolerated. The device is light weight and padded and does not disturb sleep or any other daily activities.

Sleep testing: The wearing of the sleep test device may result in decreased sleep quality for the night of testing.

Benefits

This study is not designed to benefit you directly. Your obstructive sleep apnea may improve while you are in this study but it may not. We expect that your symptoms will worsen (return to baseline) during the portion of the study in which your device is turned off.

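### 24-hour blood pressure is recorded the day after a WatchPAT night at baseline and withdrawal but 30 days after one on treatment, so any next-day effect of the test night could contribute to the pattern hypothesised in Aim 2c

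*Combined protocol and SAP*

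**What the plan says.** The Study Timeline in Section 6 pairs the sleep test and the blood pressure recording as follows.

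- Baseline: "WatchPAT baseline home sleep test (Night 1"), then "Baseline 24-hour ambulatory blood pressure monitoring (Day 2-3"). Baseline vascular tests and bloods, and device activation, are on Day 15.
- Treatment: "WatchPAT treatment home sleep test (Night 75"), then "Treatment serum biomarkers/vascular testing, 24-hour ambulatory blood pressure monitoring (Day 105-106").
- Withdrawal (therapy off Day 106-135): "WatchPAT withdrawal home sleep test (Night 135"), then "Withdrawal serum biomarkers/vascular testing, 24-hour ambulatory blood pressure monitoring (Day 136-137"). Therapy resumes on Day 137.

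Under Risks, Section 6 says of the sleep test: "The wearing of the sleep test device may result in decreased sleep quality for the night of testing". Of the equipment worn for 24 hours it says: "The device is light weight and padded and does not disturb sleep or any other daily activities". The text calls that equipment a blood flow device; I take it to be the blood pressure monitor.

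Aim 2c in Section 5 expects 24-hour blood pressure to improve on therapy and to go back to its pre-operative level after 30 days without it. There is no randomisation and no control group, and every participant passes through the phases in the same order. Section 13 describes no blood pressure analysis. The protocol gives no reason for the unequal spacing.

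**The concern.** A withdrawal phase is valuable in a single-arm study because a reversal is hard to explain by a time trend. That protection fails against a nuisance factor that switches on and off together with therapy. Here, having worn the WatchPAT the night before is such a factor for blood pressure: it is present at both off-therapy recordings and absent at the on-therapy one. The protocol itself names the sleep test as a possible disturbance of sleep and says that the 24-hour device is not one.

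If a disturbed night has any effect that raises blood pressure on the following day, part of an observed fall and return in Aim 2c could come from the test schedule. Because this would be a bias, more participants would not reduce it.

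**Working it through.** **The plan's own figure.** The only stated power is 89% for a PAT-ratio difference of 0.1 with SD 0.2, n = 40 and alpha 0.05 (Section 13). A paired normal approximation, two-sided, gives Φ(0.1/0.2 × √40 − 1.96) = Φ(1.20) = 88.5%, which reproduces it. This figure concerns the primary outcome and does not enter the present point. No power is stated for blood pressure.

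**Spacing, from the Study Timeline.**

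| Phase | WatchPAT | Blood pressure starts | Gap | Vascular tests and bloods | Gap |
|---|---|---|---|---|---|
| Baseline | Night 1 | Day 2 | 2 − 1 = 1 | Day 15 | 15 − 1 = 14 |
| Treatment | Night 75 | Day 105 | 105 − 75 = 30 | Day 105 or 106 | 30 or 31 |
| Withdrawal | Night 135 | Day 136 | 136 − 135 = 1 | Day 136 or 137 | 1 or 2 |

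**Blood pressure.** Let τ be the therapy effect (negative if therapy lowers pressure) and d the shift in the 24-hour mean on the day after a WatchPAT night. The expected values are μ + d at baseline, μ + τ on treatment and μ + d at withdrawal. Then:

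- baseline − treatment = d − τ
- withdrawal − treatment = d − τ
- withdrawal − baseline = 0

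Only d − τ can be estimated. Put another way, therapy is (0, 1, 0) and WatchPAT the night before is (1, 0, 1). Their correlation is −1, and a model with an intercept and both terms has rank 2 of 3.

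**Vascular tests and biomarkers (Aims 2a, 2b, 2d).** If these are done on Day 136, the WatchPAT pattern is (0, 0, 1). Baseline to treatment then contains τ alone, and only treatment to withdrawal contains d. The rank is 3. If they are done on Day 137, they do not follow a WatchPAT night directly.

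**Illustration of size for blood pressure.** Inputs: n = 40 (Section 9), τ = 0, and a paired t test at two-sided 0.05 (my choice, as no analysis is given). The documents state neither d nor the SD of paired differences; both are assumed. Noncentrality is d/SD × √40; for example, 2/8 × 6.32 = 1.58 gives 33.8%.

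Probability that one contrast is significant:

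| Assumed d (mmHg) | SD 6 | SD 8 | SD 10 |
|---|---|---|---|
| 0 | 5.0% | 5.0% | 5.0% |
| 0.5 | 8.1% | 6.7% | 6.1% |
| 1 | 17.7% | 12.0% | 9.5% |
| 2 | 53.8% | 33.8% | 23.5% |
| 3 | 86.9% | 63.8% | 45.7% |

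Probability that both contrasts are significant in the hypothesised direction (20,000 simulated trials per cell, independent errors at the three visits, equal d at baseline and withdrawal):

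| Assumed d (mmHg) | SD 6 | SD 8 | SD 10 |
|---|---|---|---|
| 0 | 0.4% | 0.5% | 0.4% |
| 1 | 7.2% | 3.9% | 2.7% |
| 2 | 37.3% | 18.7% | 10.8% |
| 3 | 78.8% | 47.8% | 28.9% |

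**The case against.** The strongest reply is that the mechanism is not in the documents. The Risks sentence is wording for participants. It says only that sleep may be worse, and only on the test night, whereas recording starts the next day. Nothing in the protocol says that one night in the device changes next-day pressure, or in which direction. An effect could also differ between the first and third wearing. It could be diluted too, because the 24-hour recording runs into a following night with no WatchPAT. All of this stands. The tables show what an assumed d would do; they do not show that d differs from zero.

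A reader might go further and infer that the artefact also explains the vascular and biomarker results. The documents do not support that. Baseline and treatment tests for Aims 2a, 2b and 2d are both at least 14 days from a WatchPAT night, so the improvement contrast is free of it. The timeline also gives Day 136-137 for the whole withdrawal set, so it is not settled that vascular tests and bloods fall on the day after the sleep test.

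It may also be said that this is second-order beside the missing control group and the absent blood pressure analysis. That is fair as to rank, but scheduling is the one part that cannot be repaired once the data are collected.

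**Conclusion.** The point holds as a possible bias in a secondary aim. The day gaps of 1, 30 and 1 are exact. For blood pressure, test-night proximity mirrors therapy status completely, so if a next-day rise exists, no analysis of the three planned recordings could separate it from the therapy effect. Its existence, direction and size are assumptions. At zero carry-over there is no problem; at an assumed 1 to 3 mmHg and SD 8 mmHg, the false-positive probability for one contrast would be 12% to 64%.

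For Aims 2a, 2b and 2d, at most the treatment-to-withdrawal contrast is exposed, and only if testing is on Day 136. The PAT-ratio primary outcome and its 89% power are not affected. It would be wrong to read this as showing that the blood pressure contrasts are inflated by a known amount.

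The case for changing the schedule rests on low cost, not on evidence that the bias is present.

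**What to change.** State in Section 6 that no WatchPAT falls within the two nights before any blood pressure, vascular or blood test in any phase. Two moves achieve this:

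- Baseline ambulatory blood pressure from Day 2-3 to about Day 13-14, before the Day 15 tests and activation. The gap becomes 13 − 1 = 12 days. The recording also then sits beside the other baseline tests, as in the other two phases.
- Withdrawal WatchPAT from Night 135 to about Night 133, still inside the existing Day 106-135 withdrawal period. The gap becomes 136 − 133 = 3 days.

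The treatment WatchPAT can stay at Night 75, as it is already well clear. The gaps of 12, 30 and 3 days would remain unequal, so the change removes the bias on the assumption that any effect of a test night has gone after two nights.

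Cost: the same tests, the same number of visits and no change to therapy timing. The blood pressure monitor may have to be mailed out or handed over separately from the Day 1 visit (Section 12 already covers mailing for its return). The withdrawal sleep test falls about two nights earlier, on the 28th rather than the 30th night of withdrawal.

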Subject recruitment plan: All patients in the cohort will have undergone implantation of hypoglossal nerve stimulator by the principal investigator, [name], at the Sleep Surgery Center at Emory Midtown. At their 2-week post-operative appointment, they will be approached by the research coordinator at the Emory Sleep Center regarding participation in the study.

Screening for eligibility: Eligible subjects will be identified based on a clinical chart review by the principal investigator / surgeon, [name].

Procedures when a subject withdraws from the study:

1. Once the subject expresses that he/she would like to withdraw, no further information will be collected from the subject
2. Existing data will be utilized for appropriate analyses
3. These changes will be reflected in the intention-to-treat analysis

10. Informed Consent Process

The consent process will be done in person by the research assistant.

The research assistant will remain in the patient room for an extended period of time to ensure the subject's patients are adequately answered. We will deliberately schedule these patients as the last slot in the morning clinic allowing greater than 30 minutes before the first patient in the afternoon clinic. The research assistant will also ask the subject to repeat the procedures and timeline involved in this study.

The informed consent will allow for the subject to "opt out" of certain aspects of the study. The choices will be captured in the informed consent layout.

11. Incidental Findings

We anticipate incidental findings for the 24-hour blood pressure monitoring. We will set the following parameters for which the patient will be notified and asked to contact his/her primary care physician:

- Systolic BP > 200mm Hg for greater than 60 minutes of recording time
- Diastolic BP > 160mm Hg for greater than 60 minutes of recording time

The consent will include wording to indicate that he/she may be contacted if these results are seen. The principal investigator and treating physician ([name]) will call the patient to inform him/her of the findings. The subject will be provided the option to withdraw from the study at that time.

12. Compensation

The subject will not be offered payment for being in this study. However, we will provide mailing costs for return of sleep testing and blood pressure equipment. The subject will

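### The treatment 24-hour blood pressure recording ends on the day the device is switched off (Day 106), with no read scheduled before switch-off and no investigator decision required for a subject over the Section 11 limits

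*Combined protocol and SAP*

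**What the plan says.** **Timeline (Section 6, Study Timeline).** The baseline entry is "Baseline 24-hour ambulatory blood pressure monitoring (Day 2-3", with device activation on Day 15. The treatment recording is listed as "24-hour ambulatory blood pressure monitoring (Day 105-106", and the next entry is "Therapy Withdrawal (Day 106-135". After that come "Withdrawal serum biomarkers/vascular testing, 24-hour ambulatory blood pressure monitoring (Day 136-137" and "Therapy Reactivation (Day 137". A clinic visit is listed on Day 105. No entry covers return, download or reading of the treatment recording.

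**Response to high readings (Section 11).** The limits are systolic above 200 mmHg or diastolic above 160 mmHg, each for more than 60 minutes of recording. A subject who exceeds one is called by the principal investigator, who is also the treating physician, and is asked to contact primary care. Section 11 then adds: "The subject will be provided the option to withdraw from the study at that time".

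**Equipment (Section 12).** The study pays postage for return of the blood pressure equipment.

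**What the off period is expected to do.** Section 6 (Benefits) tells subjects: "We expect that your symptoms will worsen (return to baseline) during the portion of the study in which your device is turned off". The Aim 2c hypothesis in Section 5 reads "The 24-hour ambulatory blood pressure will be improved at therapeutic levels of upper airway stimulation and returned to pre-operative levels", and places that return after the 30-day off period.

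**Entry criteria (Section 9).** Severe hypertension that is not adequately controlled is an exclusion.

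**The concern.** Switching the device off is a study procedure, done to test whether the measures go back to their untreated values. The plan expects symptoms to worsen and, under Aim 2c, expects 24-hour pressure to return to its pre-operative level. The treatment recording is the last scheduled pressure measurement before that step, so it is the natural point at which to ask whether a given subject should take it.

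As scheduled, the recording cannot serve that purpose. It finishes on the day of switch-off, and nothing makes switch-off wait for the result. Even when a flag is known, the plan asks only the subject to choose, and the choice is whether to leave the study. No physician has to record a judgement on whether the off period is acceptable. At stake is the safety of a probably small number of subjects who would lose effective therapy while their pressure is already very high.

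**Working it through.** The plan gives no figure on this point. Its one computed figure, 89% power in Section 13, does not enter. The check is day arithmetic on the Section 6 timeline, followed by the cost of a change.

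**Gaps in the current schedule**

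| Interval | Calculation | Result |
|---|---|---|
| End of treatment recording to switch-off | 106 - 106 | 0 days |
| End of baseline recording to activation, for comparison | 15 - 3 | 12 days |
| Length of off period, counted inclusively | 135 - 106 + 1 | 30 days |
| Switch-off to start of next scheduled recording | 136 - 106 | 30 days |
| Switch-off to reactivation | 137 - 106 | 31 days |
| End of baseline recording to switch-off | 106 - 3 | 103 days |

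The Day 105 clinic visit cannot act as the review, because the recording does not end until Day 106. Handing the equipment back and reading it on Day 106 is possible, but the plan does not schedule it, and posted return makes a same-day read less likely.

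**Who decides, under each route in the plan**

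- Section 11: a physician's call, a referral, and the subject's option to withdraw.
- Section 10: subjects may opt out of parts of the study. This is also the subject's choice, captured in the consent form. Consent is on Day 1, before any recording.
- Section 9: the hypertension exclusion. This is a criterion for entry, and nothing reapplies it before switch-off.

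None of these requires an investigator's decision about the off period.

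**Effect of delaying switch-off by s days** (assumption: s = 2 to 7)

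- Switch-off: 106 + s = Day 108 to 113.
- Home sleep test at the end of the off period: 135 + s = Night 137 to 142.
- Start of off-period testing: 136 + s = Day 138 to 143.
- Reactivation: 137 + s = Day 139 to 144.
- Time from switch-off to reactivation: (137 + s) - (106 + s) = 31 days, unchanged.
- Added follow-up: s/137 = 2/137 = 1.5% to 7/137 = 5.1%.

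**Effect on the return comparison in Aim 2c** (assumption: k = 0 to 3 of the 40 completers omit the off period, with the standard deviation of the change unaffected)

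- Standard error ratio = sqrt(40/(40 - k)).
- k = 0: 1.000. k = 1: sqrt(40/39) = 1.013. k = 3: sqrt(40/37) = 1.040.
- The standard error therefore rises by 0% to 4.0%. The omitted subjects would probably be those with the highest pressures, so their number should be reported.

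**The case against.** The strongest reply is that the plan already has a response and that it does not lapse at switch-off. Once the Day 105-106 recording is read, Section 11 requires the treating physician to call, refer and offer withdrawal, whether or not the device is already off. That physician can use clinical judgement on the call. Switch-off is reversible, and nothing in the plan forbids early reactivation. This stands, and it limits the point.

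A reader might infer from the 30-day gap that a flagged subject would go unnoticed until Day 136, or be held off therapy until Day 137. The documents do not support either inference. If reading took the assumed 2-7 days, the call would come about 2-7 days into the off period. What remains is that no read deadline guarantees this, and that the response does not include a required decision on the off period.

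A reader might also infer that a baseline flag carries the same weight. It does not. A baseline flag leaves 103 days for the call and referral to take effect, with a clinic visit on Day 105, and the off period is expected to return the subject to the untreated state in which the baseline recording was made. Such a subject might also meet the entry exclusion. The baseline case justifies only that the same documented decision be made.

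Finally, flags at these limits may never occur in a cohort that excludes severe, poorly controlled hypertension. That is fair. The documents give no frequency, and none is claimed here.

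**Conclusion.** The point holds as a gap in safety procedure. If the plan is followed exactly, a subject above the Section 11 limits while on therapy can enter the off period with the recording unread (0 days between recording end and switch-off), and no investigator decision is required before or after. The existing call, referral and offer to withdraw reduce the exposure but have no deadline, and the next scheduled recording begins 30 days after switch-off.

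The number of subjects affected is unknown, likely small and possibly zero. The 2-7 days for reading and the 0-3 subjects omitting the off period are assumptions used only to size the cost of a change. The Section 13 analysis of stimulation level against PAT ratio does not name the off-period night, so no loss of power is claimed for it. The change is worth making because it costs little and protects subjects during a step that the study itself imposes. Confidence is medium.

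**What to change.** Amend Section 11 and the Section 6 timeline as follows.

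1. Read the Day 105-106 recording against the Section 11 limits before switch-off. Make this a safety read, separate from the blinded interpretation of the tests.
2. For any subject flagged at that read, or flagged at baseline, require a documented investigator decision before switch-off: proceed with, defer or omit the off period.
3. Start the off period only after the read. Move Night 135, Day 136-137 and reactivation by the same number of days, so that the off period keeps its length.
4. Keep subjects whose off period is omitted in the baseline-to-treatment comparison, and report how many there are.

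**Cost.** The study needs a deadline for equipment return, and each subject stays in it a few days longer: 1.5%-5.1% more follow-up for an assumed delay of 2-7 days. The return-to-baseline comparison may lose a few subjects. With 0-3 of 40 assumed, its standard error rises by at most 4.0%. No new test or procedure is needed.

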Obstructive sleep apnea (OSA), repetitive collapse of the upper airway during sleep, represents a growing individual and public health concern. This disease negatively impacts patients' sleep quality and daytime function, including 3-10 fold increased risk of motor vehicle accidents. Several large, longitudinal cohorts have consistently demonstrated deleterious effects of OSA on cardiovascular health, including elevated rates of incident hypertension, myocardial infarction and cerebrovascular accidents. The link between OSA and cardiovascular consequences can be largely explained by autonomic imbalance during repeated episodes of nocturnal airway obstruction. Compared to controls, patients with OSA have increased sympathetic activity when awake, with further elevation of both sympathetic activity and blood pressure during sleep. Multiple physiologic mechanisms are responsible for these autonomic changes during obstructive episodes including the interaction of baroreceptors, chemoreceptors and respiratory afferent receptors. Positive airway pressure (PAP) serves as a pneumatic stent for the airway, maintaining airway patency and normoxia. PAP therapy has demonstrated consistent, meaningful reductions in sympathetic overactivity during wake and sleep.

Though PAP therapy is highly efficacious, fewer than 50% of patients are adequately treated due to adherence difficulty. In 2014, the Federal Drug Administration approved hypoglossal nerve stimulation (HGNS) for the treatment of patients with moderate-severe OSA unable to adequately use PAP. Recently published three-year data for this therapy demonstrated stable, marked improvement in key polysomnography indices, sleepiness measures and functional outcomes with adherence greater than 80%. To date, however, no study has examined cardiovascular endpoints of HGNS therapy in OSA patients.

Our overarching aim is to evaluate the effect of HGNS therapy on autonomic and vascular function as measured by changes in peripheral arterial tonometry, flow mediated dilation, peripheral arterial stiffness, 24-hour ambulatory blood pressure, 7-day dysrhythmia monitor and serum biomarkers before, during and after treatment in this high-risk cardiovascular population. **We hypothesize that all aforementioned measurements will be significantly improved following HGNS therapy and return to baseline values following a therapy withdrawal period.**

5. Objectives

Aim 1

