also be provided lunch and parking vouchers for each time (3 in total) that he/she undergoes cardiovascular testing. The subject will not be responsible to pay for any cardiovascular testing as this is being done outside routine clinical care.

13. Statistical Analysis

With 40 subjects, we will have 89% power to detect a difference of 0.1 in the PAT ratio (primary outcome) with a standard deviation of 0.2 and alpha of 0.05.

Each subject will have a baseline PAT ratio derived from the average of the 10 obstructive events without stimulation (Aim 1). The PAT ratios at each stimulation level (5-7 stimulation levels based on previous experience) will be averaged from 5 obstructive events at each level. With greater than 30 data points per individual, linear regression will be performed for each subject with stimulation level as the main effect variable and PAT ratio as the outcome variable. We will determine if stimulation level is positively associated with PAT ratio. We will also perform linear regression, in a similar manner, from the combined values of the cohort to determine an effect at the sample level.

An interim analysis will not be performed as the primary outcome variable is largely observational (non-interventional); thus, the findings are expected during the treatment of moderate-severe obstructive sleep apnea

14. Data Safety and Monitoring Board

A DSMB will not be required. Access to this database will be restricted by a database manager and will be password protected. The only individuals who will be able to see patient identifiers, like name, address, and social security number, will be the Principal Investigator, research coordinators, recruiters and the database managers. Other investigators will have different passwords that will provide restricted access to the database. Those with restricted access will be able to query the database for scientific information/variables, but will not be able to view information on patient identifiers such as name, address, and social security number. If investigators with restricted access want to conduct studies which require them to obtain patient identifiers so that patients can be contacted for follow-up information/follow-up visits, these investigators will have to submit a separate protocol to IRB to get permission to obtain patient identifiers and contact patients.

15. Confidentiality

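### The 89% power in Section 13 belongs to a mean-difference test that the plan does not describe; the planned cohort regression states no subject term, so its error rate is not controlled

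*Combined protocol and SAP*

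**What the plan says.** Section 13 (Statistical Analysis) opens with the power claim: "With 40 subjects, we will have 89% power to detect a difference of 0.1 in the PAT ratio (primary outcome"), using an SD of 0.2 and alpha of 0.05. It names no test, no pair of conditions and no sidedness. It does not say whether 0.2 is the SD of a change or of a single measurement.

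The section then defines an unstimulated baseline from 10 events, tied to Aim 1. At each of 5-7 stimulation levels the PAT ratio "will be averaged from 5 obstructive events at each level". The analyses are:

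- Per subject: "linear regression will be performed for each subject with stimulation level as the main effect variable and PAT ratio as the outcome variable". The amount of data for this is described as "With greater than 30 data points per individual". The stated purpose is "We will determine if stimulation level is positively associated with PAT ratio".
- Cohort: a regression done in the same way, "from the combined values of the cohort to determine an effect at the sample level".

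No subject effect, clustered standard error or rule for combining the per-subject regressions is stated. The Aim 1 hypothesis in Section 5 is about improvement as stimulation rises, which is a slope. Section 9 expects 40 completers from 50 enrolled.

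**The concern.** A power figure is informative only for the test it was computed for. Here the figure fits a single mean difference, while every planned analysis estimates a slope, and no target slope or slope SD is given. A reader therefore cannot tell what chance the primary analysis has of succeeding.

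The cohort regression is the only analysis that yields a result at the sample level. It pools many values from each of 40 people. If they are treated as independent, the standard error is wrong, and the direction depends on how subjects differ. Differences in overall PAT ratio inflate the residual variance and make the test conservative. Differences in slope make the estimate more variable than its standard error shows and make the test liberal. The first kind of error can hide a real effect; the second can declare one that is not there.

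**Working it through.** **1. The plan's own figure.** Inputs from Section 13: n = 40, difference 0.1, SD 0.2, alpha 0.05.

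- Two-sided one-sample/paired z: Φ(0.1/(0.2/√40) − 1.96) = Φ(3.162 − 1.96) = 88.5%, which rounds to 89%.
- Same contrast by noncentral t, 39 df: 86.9%.
- One-sided: 93.5% (z), 92.8% (t).
- Two independent groups, two-sided: 35% (20 per group), 61% (40 per group).

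Only the paired or one-sample form fits. If 0.2 is a single-measurement SD, the SD of the difference is 0.2√(2(1−ρ)), and t power is 59%, 74%, 87% and 93% at ρ = 0, 0.3, 0.5 and 0.6. No ρ is given.

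**2. Rows in the pooled regression.** Events: 10 + 5×5 = 35 to 10 + 5×7 = 45 per subject, or 1,400-1,800 in all. Level averages including baseline: 6-8 per subject, or 240-320 in all. More than 30 points per person fits events only; the averaging sentence fits averages.

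**3. Error rate of the pooled regression.** Assumed, because the documents give none: intercept SD a, slope SD τ, event SD e, with level scaled 0-1. Take 6 levels for everyone and event rows. The mean of x is 0.4375, the mean of x² is 0.316, and Sxx = 4.983.

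- True SE of the slope: √[(τ² + e²/Sxx)/40].
- SE the pooled fit reports, approximately: √[(a² + 0.316τ² + e²)/(40 Sxx)].

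With a = τ = e = 0.2:

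- True SE: √[(0.04 + 0.00803)/40] = 0.0347.
- Reported SE: √[(0.04 + 0.0126 + 0.04)/199.3] = 0.0216.
- The ratio is 0.62, so the nominal 5% becomes 2(1 − Φ(1.96×0.62)) = 22%.

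With τ = 0 and a = e = 0.2, the true SE is 0.0142 against 0.0200 reported. The ratio is 1.41 and the rate is 0.6%.

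Simulation (true mean slope 0, 4,000 runs, 6 levels) agrees:

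| a, τ, e | Pooled, events | Pooled, averages |
|---|---|---|
| 0.2, 0, 0.2 | 0.6% | 0% |
| 0.2, 0.1, 0.2 | 6.2% | 0.1% |
| 0.1, 0.1, 0.1 | 23% | 1.7% |
| 0.2, 0.2, 0.2 | 22% | 1.3% |
| 0.15, 0.2, 0.2 | 27% | 3.9% |
| 0.15, 0.2, 0.1 | 37% | 3.9% |
| 0.1, 0.2, 0.1 | 44% | 8.5% |

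A t-test on the 40 subject slopes gave 4.6%-5.8% throughout. With seven levels for everyone, the last row rises to about 46% and just over 9%. If subjects have differing numbers of levels (5-7, on a common scale), it becomes 48% and 13%, with the slope t-test at 4.6%-6.0%.

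**4. Power of the pooled regression on averages**, mean slope 0.1, a = e = 0.2, 6 levels, against the slope t-test:

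- τ = 0.2: about 61%-64% against 76%-80% (separate simulations).
- τ = 0.1: 82% against 99%.
- τ = 0: 93% against 100%.

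**5. Power of the slope t-test for a mean full-range change of 0.1.**

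- If 0.2 is the SD of the observed full-range change: 87%.
- If 0.2 is the true between-subject slope SD, event noise adds to it. With 6 levels and event rows, e = 0.1 gives √(0.04 + 0.01/4.983) = 0.205 and 85%; e = 0.2 gives √(0.04 + 0.04/4.983) = 0.219 and 80%. Over 5-7 levels and both row types the range is 79%-85%.

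**The case against.** The strongest reply has four parts.

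- **The arithmetic is right, and the text is silent rather than wrong.** Section 13 neither includes nor rules out a subject term, and the paired form is inferred from matching the number. This stands. The defect is that the test, the SD and the handling of repeated values are not stated.
- **The error rate is not always wrong.** This also stands: some settings fall near 5%, such as 6.2% on events and 3.9% on averages. A reader might infer that the test necessarily fails, or quote rates of 50% or more. Those need an intercept SD of only 0.05 with slope SD 0.2, a corner that the documents give no reason to prefer.
- **The power loss can be exaggerated.** A contrast of 6% against 91% arises at a slope of 0.05, half the plan's 0.1, with no slope variation. At 0.1 the same setting gives 93% against 100%. The loss at slope SD 0.2 remains.
- **The primary analysis is not wide open.** Section 4 does aim to "evaluate the effect of HGNS therapy on autonomic and vascular function as measured by changes in peripheral arterial tonometry", "before, during and after treatment in this high-risk cardiovascular population", and the timeline schedules WatchPAT nights. A reader might infer that the powered difference is WatchPAT Night 1 versus Night 75. Nothing ties the 0.1 or the 0.2 to those nights, and Section 4 is a general aim over several measures. The Aim 1 hypothesis and the regression text in Section 13 point to the slope.

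None of this supplies a power figure for the slope or a way of handling repeated values.

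**Conclusion.** The point holds in this form: the 89% is sound arithmetic for a mean difference that the plan does not test, and the cohort regression as written does not control its error rate. With intercept SD 0.1-0.2 and the same number of levels for everyone, that rate ranges from about 1% to 46% on event rows and about 0% to 9% on averages; a test on subject slopes stays near 5%. At a slope of 0.1 with slope SD 0.2 and intercept SD 0.2, using averages costs about 15 points of power. With little slope variation the loss is smaller.

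The mismatch between power and analysis, and the missing subject term, rest on the text alone. The sizes rest on assumed variances and on independent intercepts and slopes. The documents do not show that the study is underpowered: properly analysed, the slope has 79%-87% power under the readings of SD 0.2 as a change or slope SD. The section should be corrected before analysis.

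**What to change.** In Section 13:

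1. Replace the pooled regression with one named analysis that accounts for subject: a one-sample t-test on the 40 subject slopes, or a mixed model with random intercept and slope per subject. A subject intercept alone is not enough: with slope SD 0.2 it left simulated error rates of 23%-41%. Put stimulation level on one stated scale common to all subjects, and say whether rows are events or level averages.
2. Name the Aim 1 slope as the primary test.
3. Restate the power for that test, with the sidedness and the meaning of SD 0.2. By two-sided t it is 87% if 0.1 and 0.2 are the mean and SD of the observed full-range change within subject, and about 79%-85% if 0.2 is the true between-subject slope SD (event SD 0.2 to 0.1, assumed).

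If a paired contrast is kept instead, it should compare no stimulation with a stated stimulation level, as Section 13 defines them. A contrast of WatchPAT Night 1 with Night 75 would need its own target and SD.

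Cost: wording in Section 13, with no added patients or visits. The stated power becomes slightly less favourable, and the sponsor must supply a slope target and SD that the documents do not give.
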